4.1 Description of study design

This open label, single-arm, multi-center study to evaluate the efficacy and safety of deferasirox in NTDT patients with iron overload will include the following phases:

Screening (4 weeks) to determine patient eligibility

Open label treatment with deferasirox:

- Starting dose 10 mg/kg/day for 4 weeks;
- At Week 4, dose adjustments according to baseline LIC:
 - 20 mg/kg/day for patients with baseline LIC > 15 mg Fe/g dw
 - 15 mg/kg/day for patients with baseline LIC > 7 but ≤ 15 mg Fe/g dw
 - Dose will remain at 10 mg/kg/day for patients with baseline LIC ≥ 5 but ≤ 7 mg Fe/g dw
- Approximately every 6 months, starting at Week 24, dose adjustments according to LIC:
 - Increase dose by 5-10 mg/kg/day, if LIC > 15 mg Fe/g dw, maximum of 30 mg/kg/day
 - May increase dose by 5 mg/kg/day if LIC >7 but ≤ 15 mg Fe/g dw, maximum of 20 mg/kg/day
 - Same dose if LIC is ≥3 but ≤ 7 mg Fe/g dw, maximum of 10 mg/kg/day

The maximum dose of deferasirox throughout the study will be 30 mg/kg/day.

If LIC measurement is <3 mg Fe/g dw or SF is <300 ng/mL, treatment will be interrupted. Patients who have interrupted study treatment during the first year of the study due to LIC <3 mg Fe/g dw or SF <300 ng/mL will continue the monthly visit schedule. Patients who have treatment interruption due to LIC <3 mg Fe/g dw or SF <300 ng/mL after 52 weeks, will complete scheduled visit one month post-interruption and then be followed every three months.

Study treatment will restart at the previous effective dose when LIC ≥5 mg Fe/g dw and SF ≥ 300 ng/mL (maximum of 10 mg/kg/day). Once on treatment, patients will be followed monthly.

See [Figure 4-1](#), for study design schematic.

[figure not shown]
[figure not shown]

Figure 4-1 Study Design

Approximately 117 patients will be enrolled. Treatment duration will be five years. Pharmacokinetic analysis will be conducted in a subset of 20 patients from selected participating centers.

4.2 Timing of interim analyses and design adaptations

No formal interim analysis based on primary endpoint will be performed.

Some basic safety annual analyses will be performed for PSUR (Periodic Safety Update Report).

4.3 Definition of end of the study

Patients will be followed up to five years. Completion of this study as a whole will occur after the last visit of the last patient of the study and upon the availability and accuracy verification of the last data point required for final statistical analysis.

4.4 Early study termination

The study can be terminated at any time for any reason by Novartis. Should this be necessary, the patient should be seen as soon as possible. The site will contact the patient, schedule a final visit and provide instruction to discontinue study drug administration. The same assessments must be performed as described in [Section 7](#) for a prematurely withdrawn patient. The investigator may be informed of additional procedures to be followed in order to ensure that adequate consideration is given to the protection of the patient's interests. The

investigator will be responsible for informing IRBs and/or ECs of the early termination of the trial.

5 Population

5.1 Patient population

Approximately 117 patients will be enrolled in this trial.

The investigator or designee must ensure that only patients who meet all the following inclusion and none of the exclusion criteria are offered enrollment in the study.

5.2 Inclusion criteria

Patients eligible for inclusion in this study must meet **all** of the following criteria:

- Male or female aged ≥ 10 years with non-transfusion-dependent congenital or chronic anemias inclusive of beta-thalassemia intermedia, HbE beta-thalassemia or alpha-thalassemia intermedia (HbH disease)
- LIC ≥ 5 mg Fe/g dw measured by R2 MRI at screening
- Serum ferritin ≥ 300 ng/mL at screening (two consecutive values at least 14 days apart from each other)
- Written informed consent obtained prior to any screening procedures

5.3 Exclusion criteria

Patients eligible for this study must not meet **any** of the following criteria:

- Patients diagnosed with HbS-beta Thalassemia
- Anticipated regular transfusion program during the study. Patients having a sporadic transfusion (e.g. in case of infection) during the course of the study will not be excluded
- Any blood transfusion 6 months prior to study start
- Patients unable to undergo study assessments including MRI, e.g. who are claustrophobic to MRI, have a cardiac pacemaker, ferromagnetic metal implants other than those approved as safe for use in MR scanners (Example: some types of aneurysm clips, shrapnel), and patients who are obese (exceeding the equipment limits)
- Significant proteinuria as indicated by a urine protein/urine creatinine ratio > 1.0 mg/mg in a non-first void urine sample at visit 1 or visit 2 (or alternatively in two of three samples obtained for screening)
- Creatinine clearance ≤ 40 ml/min on two measurements during visit 1 and visit 2
- Serum creatinine $> \text{ULN}$ on two measurements during visit 1 and visit 2
- ALT $> 5 \times \text{ULN}$ at visit 1 and visit 2
- Clinical evidence of active hepatitis B (positive HBsAg with negative HBsAb) or hepatitis C (positive HCV antibody and detectable HCV RNA with ALT above the normal range) (Note: Hepatitis B carriers will be allowed to enter the trial.)
- Known diagnosis of cirrhosis (confirmed by biopsy if available)

- A history of clinically relevant ocular and/or auditory toxicity related to iron chelation therapy
- History of positive HIV serology (ELISA or Western blot)
- Presence of a surgical or medical condition that might significantly alter the absorption, distribution, metabolism or excretion of the study drug
- Patients with active inflammatory diseases that interferes with the accurate measurement of serum ferritin
- Pregnant or breast feeding patients, or patients of child-bearing potential not employing an effective method of birth control. (See [Women of child-bearing potential](#), below, for further details regarding effective methods of birth control.)
- Patients participating in another clinical trial or receiving a systemic investigational drug within the past 4 weeks or topical investigational drug within the past 7 days of screening
- History of non-compliance with medical regimens or patients who are considered potentially unreliable and/or not cooperative, unwilling or unable to comply with the protocol
- History of hypersensitivity to any of the study drug or excipients
- Significant medical condition interfering with the ability to partake in this study (e.g. systemic uncontrolled hypertension, unstable cardiac disease not controlled by standard medical therapy, systemic disease (cardiovascular, renal, hepatic, etc.)
- History of drug or alcohol abuse within the 12 months prior to enrollment

[figure not shown]
Women of child-bearing potential

Women of child-bearing potential, defined as all women physiologically capable of becoming pregnant, including female adolescents who are menarchal or who become menarchal during the study, unless they are using effective methods of contraception during dosing of study treatment.

Effective contraception methods include:

1. Total abstinence: When this is in line with the preferred and usual lifestyle of the patient. Periodic abstinence (e.g., calendar, ovulation, symptothermal, post-ovulation methods) and withdrawal are not acceptable methods of contraception.
2. Female sterilization: have had surgical bilateral oophorectomy (with or without hysterectomy) or tubal ligation at least six weeks prior to study. In case of oophorectomy alone, only when the reproductive status of the woman has been confirmed by follow up hormone level assessment.
3. Male partner sterilization (at least 6 months prior to screening). For female study subjects, the vasectomized male partner must be the sole partner for that patient.
4. Barrier methods of contraception: condom or occlusive cap (diaphragm or cervical/vault caps) with spermicidal foam/gel/film/cream/ vaginal suppository.
5. Placement of an intrauterine device (IUD) or intrauterine system (IUS).

Women are considered to be not of child bearing potential if they have had 12 months of natural (spontaneous) amenorrhea with an appropriate clinical profile (e.g. age appropriate,

history of vasomotor symptoms) or have had surgical bilateral oophorectomy (with or without hysterectomy) or tubal ligation at least six weeks ago. In the case of oophorectomy alone, only when the reproductive status of the patient has been confirmed by follow up hormone level assessment is she considered not of child bearing potential.

The use of hormonal contraceptives (oral or injected) is prohibited in this study due to a decrease in efficacy when used in combination with deferasirox.

5.4 Exclusion criteria for pediatric patients

- A patient's weight of at least 20 kg is required to allow dosing of 5 mg/kg with one tablet of 125 mg

6 Treatment

6.1 Investigational treatment, other study treatment, supportive treatment

The investigational study drug used in this trial is deferasirox [ICL670, Exjade[®]]. Deferasirox will be initially administered by oral daily dosing of 10 mg/kg/day. After four weeks, the dose of deferasirox may be adjusted according to baseline LIC assessment; further dose adjustments may occur approximately every 6 months (starting at Week 24), up to five years, based upon LIC measurement (see [Section 6.1.1](#)).

Deferasirox [ICL670, Exjade[®]] will be provided as 125 mg, 250 mg, and 500 mg dispersible tablets packaged, labeled and supplied to the local Country Pharma Organizations, which will further distribute them to the study centers. Study medication will be open label.

Immediately before dispensing the package to the patient, investigator staff will detach the tear-off part of the label from the packaging and affix it to the source document (Drug Label Form) containing patient's unique number.

Definition of terms:

- Study drug:
deferasirox (ICL670, Exjade[®]) 125mg, 250mg and 500mg tablets for oral use
- Study treatment:
Starting dose: 10 mg/kg/day p.o. deferasirox

6.1.1 Dosing regimen

The starting dose of deferasirox for all patients will be 10 mg/kg/day for 4 weeks.

- After 4 weeks, the dose of deferasirox will be adjusted according to baseline LIC measurements:
 - 20 mg/kg/day for patients with baseline LIC > 15 mg Fe/g dw
 - 15 mg/kg/day for patients with baseline LIC > 7 but ≤ 15 mg Fe/g dw
 - Dose will remain at 10 mg/kg/day for patients with baseline LIC ≥ 5 but ≤ 7 mg Fe/g dw

- Approximately every 6 months (starting at Week 24), the dose of deferasirox will be further adjusted, according to the following LIC measurements:
 - Increase dose by 5-10 mg/kg/day if LIC is > 15 mg Fe/g dw, maximum of 30 mg/kg/day
 - May increase dose by 5 mg/kg/day if LIC is > 7 but ≤ 15 mg Fe/g dw, maximum of 20 mg/kg/day. Same dose if LIC is ≥ 3 but ≤ 7 mg Fe/g dw, maximum of 10 mg/kg/day

Patients who have been dose escalated will be monitored every week for four weeks after the escalation, to assess serum creatinine. Serum transaminases, bilirubin, and alkaline phosphatase will be assessed two weeks following dose escalation. This may be conducted at the local lab. After these periods (if they are applicable), the patient will visit the study center according to the monthly visit schedule.

If LIC measurement is < 3 mg Fe/g dw or SF is < 300 ng/mL, treatment will be interrupted. Patients will continue with visits during the period of treatment interruption and study treatment will restart at the previous effective dose when LIC ≥ 5 mg Fe/g dw and SF is ≥ 300 ng/mL (maximum of 10 mg/kg/day).

Dose adjustments based on safety issues are allowed in the study at any time. Investigator can reduce or interrupt study treatment and recommendations for such dose adjustments are described in [Section 6.4](#).

The maximum dose of deferasirox throughout the study will be 30 mg/kg/day.

Study Drug Administration

The patient will be instructed how to prepare his/her daily dose from the three tablet strengths of deferasirox [ICL670, Exjade[®]] available (125 mg, 250 mg, 500 mg). The dose will be assigned based on the patient's weight (see [Table 6-1](#) through to [Table 6-6](#)). Given the available strengths of deferasirox tablets, the patient's daily dose will be rounded to the nearest whole tablet size (relative to a 125 mg tablet).

Each time study medication is dispensed to the patient and/or the legal guardian, the investigator will provide detailed instructions on how to prepare and administer deferasirox.

At regular site visits the investigator or pharmacist will dispense to the patient and/or the legal guardian, an appropriate number of deferasirox bottles (see [Table 6-1](#) through to [Table 6-6](#)) from a choice of 125 mg, 250 mg, 500 mg strengths, based on the patient's calculated daily dose. Date and visit number must be recorded onto the trial drug label when dispensing the drug. The number of tablets of each strength dispensed will be recorded in the study drug dosing log. All deferasirox bottles (opened and unopened) returned by the patient will be counted and the sum entered into the study drug dosing log by the investigator or pharmacist at the study site.

Medication labels will comply with the legal requirements of the countries where the study is implemented and be printed in the local language. They will supply no information about the patient. Only the subject identifier will be entered on the medication label by the investigator or pharmacist before the corresponding medication is handed out to the patient. The storage conditions and the expiration date for study drug will be described on the medication label.

Patient Information

The investigator must instruct the patient to take the study drug exactly as prescribed. All dosages prescribed and dispensed to the patient and all dose changes during the study must be recorded on the Dosage Administration Record electronic case report form (eCRF).

Deferasirox must be taken orally, once daily, on an empty stomach, at least 30 minutes before food and no less than 2 hours after the last food intake, preferable at the same time each day. The tablets are dispersed by stirring in a glass of water or orange or apple juice (100 ml to 200 ml) until a fine suspension is obtained. For daily doses less than 1 g, the tablets should be dispersed in at least 100 ml, and for daily doses from 1 g to 3 g, the tablets should be dispersed in at least 200 ml. Following full disintegration of the tablets, the liquid should be consumed promptly. Any residue in the glass and/or on the stirrer must be dispersed in additional liquid and swallowed.

The individual daily dose of deferasirox will be determined by the investigator and the amount of tablets corresponding to this dose will be calculated based on the patient's body weight (see [Table 6-1](#) through to [Table 6-6](#)).

Patient Numbering

Each patient in the study is uniquely identified by a **9 digit patient number** which is a combination of his/her **4-digit center number** and **5-digit subject number**. The center number is assigned by Novartis to the investigative site.

When the patient has signed the informed consent form, the patient is assigned a patient number by the investigator. At each site, the first patient is assigned patient number 1, and subsequent patients are assigned consecutive numbers (e.g., the second patient is assigned patient number 2, the third patient is assigned patient number 3). The assigned patient number should be entered in the field labeled "Subject ID" on the electronic data capture (EDC) data entry screen.

Once assigned to a patient, the patient number will not be reused. If the patient fails to be enrolled, the patient is deemed a screen failure. In addition, the Screening Log will be completed for these patients.

Re-screened patients will be provided a new patient number.

Deferasirox dosing tables and guidance

Table 6-1 Deferasirox dosing table for 5 mg/kg/day

| Pt Weight in kg | Closest Dose | 125 mg | 250 mg | 500 mg |
|-----------------|--------------|--------|--------|--------|
| 20 - 37.5 | 125 | 1 | | |
| 37.6 - 62.5 | 250 | | 1 | |
| 62.6 - 87.5 | 375 | 3 | | |
| 87.6 - 112.5 | 500 | | | 1 |
| 112.6 - 137.5 | 625 | 1 | | 1 |

Table 6-2 Deferasirox dosing table for 10 mg/kg/day

| Pt Weight in kg | Closest Dose | 125 mg | 250 mg | 500 mg |
|-----------------|--------------|--------|--------|--------|
| 20 - 31.3 | 250 | 2 | | |
| 31.4 - 43.8 | 375 | 3 | | |
| 43.9 - 56.3 | 500 | | | 1 |
| 56.4 - 68.8 | 625 | 1 | | 1 |
| 68.9 - 81.3 | 750 | | 1 | 1 |
| 81.4 - 93.8 | 875 | 3 | | 1 |
| 93.9 - 106.3 | 1000 | | | 2 |
| 106.4 - 118.8 | 1125 | 1 | | 2 |

Table 6-3 Deferasirox dosing table for 15 mg/kg/day

| Pt Weight in Kg | Closest Dose | 125 mg | 250 mg | 500 mg |
|-----------------|--------------|--------|--------|--------|
| 20 - 20.8 | 250 | 2 | | |
| 20.9 - 29.2 | 375 | 3 | | |
| 29.3 - 37.5 | 500 | | | 1 |
| 37.6 - 45.8 | 625 | 1 | | 1 |
| 45.9 - 54.2 | 750 | | 1 | 1 |
| 54.3 - 62.5 | 875 | 3 | | 1 |
| 62.6 - 70.8 | 1000 | | | 2 |
| 70.9 - 79.2 | 1125 | 1 | | 2 |
| 79.3 - 87.5 | 1250 | | 1 | 2 |
| 87.6 - 95.8 | 1375 | 3 | | 2 |
| 95.9 - 104.2 | 1500 | | | 3 |
| 104.3 - 112.5 | 1625 | 1 | | 3 |
| 112.6 - 120.8 | 1750 | | 1 | 3 |

Table 6-4 Deferasirox dosing table for 20 mg/kg/day

| Pt Weight in Kg | Closest dose | 125 mg | 250 mg | 500 mg |
|-----------------|--------------|--------|--------|--------|
| 20.0 - 21.9 | 375 | 3 | | |
| 22.0 - 28.1 | 500 | | | 1 |
| 28.2 - 34.4 | 625 | 1 | | 1 |
| 34.5 - 40.6 | 750 | | 1 | 1 |
| 40.7 - 46.9 | 875 | 3 | | 1 |
| 47.0 - 53.1 | 1000 | | | 2 |
| 53.2 - 59.4 | 1125 | 1 | | 2 |
| 59.5 - 65.6 | 1250 | | 1 | 2 |
| 65.7 - 71.9 | 1375 | 3 | | 2 |
| 72.0 - 78.1 | 1500 | | | 3 |
| 78.2 - 84.4 | 1625 | 1 | | 3 |
| 84.5 - 90.6 | 1750 | | 1 | 3 |
| 90.7 - 96.9 | 1875 | 3 | | 3 |
| 97.0 - 103.1 | 2000 | | | 4 |
| 103.2 - 109.4 | 2125 | 1 | | 4 |
| 109.5 - 115.6 | 2250 | | 1 | 4 |
| 115.7 - 121.9 | 2375 | 3 | | 4 |

[figure not shown]

Table 6-5 Deferasirox dosing table for 25 mg/kg/day

| Pt Weight in Kg | Closest dose | 125 mg | 250 mg | 500 mg |
|-----------------|--------------|--------|--------|--------|
| 20.0 - 22.5 | 500 | | | 1 |
| 22.6 - 27.5 | 625 | 1 | | 1 |
| 27.6 - 32.5 | 750 | | 2 | 1 |
| 32.6 - 37.5 | 875 | 3 | | 1 |
| 37.6 - 42.5 | 1000 | | | 2 |
| 42.6 - 47.5 | 1125 | 1 | | 2 |
| 47.6 - 52.5 | 1250 | | 1 | 2 |
| 52.6 - 57.5 | 1375 | 3 | | 2 |
| 57.6 - 62.5 | 1500 | | | 3 |
| 62.6 - 67.5 | 1625 | 1 | | 3 |
| 67.6 - 72.5 | 1750 | | 1 | 3 |
| 72.6 - 77.5 | 1875 | 3 | | 3 |
| 77.6 - 82.5 | 2000 | | | 4 |
| 82.6 - 87.5 | 2125 | 1 | | 4 |
| 87.6 - 92.5 | 2250 | | 1 | 4 |
| 92.6 - 97.5 | 2375 | 3 | | 4 |
| 97.6 - 102.5 | 2500 | | | 5 |
| 102.6 - 107.5 | 2625 | 1 | | 5 |
| 107.6 - 112.5 | 2750 | | 1 | 5 |
| 112.6 - 117.5 | 2875 | 3 | | 5 |
| 117.6 - 122.5 | 3000 | | | 6 |

Table 6-6 Deferasirox dosing table for 30 mg/kg/day

| Pt Weight in Kg | Closest Dose | 125mg | 250 mg | 500 mg |
|-----------------|--------------|-------|--------|--------|
| 20.0 - 22.9 | 625 | 1 | | 1 |
| 23.0 - 27.1 | 750 | | 1 | 1 |
| 27.2 - 31.3 | 875 | 3 | | 1 |
| 31.4 - 35.4 | 1000 | | | 2 |
| 35.5 - 39.6 | 1125 | 1 | | 2 |
| 39.7 - 43.8 | 1250 | | 1 | 2 |
| 43.9 - 47.9 | 1375 | 3 | | 2 |
| 48.0 - 52.1 | 1500 | | | 3 |
| 52.2 - 56.3 | 1625 | 1 | | 3 |
| 56.4 - 60.4 | 1750 | | 1 | 3 |
| 60.5 - 64.6 | 1875 | 3 | | 3 |
| 64.7 - 68.8 | 2000 | | | 4 |
| 68.9 - 72.9 | 2125 | 1 | | 4 |
| 73.0 - 77.1 | 2250 | | 1 | 4 |
| 77.2 - 81.3 | 2375 | 3 | | 4 |
| 81.4 - 85.4 | 2500 | | | 5 |
| 85.5 - 89.6 | 2625 | 1 | | 5 |
| 89.7 - 93.8 | 2750 | | 1 | 5 |
| 93.9 - 97.9 | 2875 | 3 | | 5 |
| 98.0 - 102.1 | 3000 | | | 6 |
| 102.2 - 106.3 | 3125 | 1 | | 6 |

| Pt Weight in Kg | Closest Dose | 125mg | 250 mg | 500 mg |
|-----------------|--------------|-------|--------|--------|
| 106.4 - 110.4 | 3250 | | 1 | 6 |
| 110.5 - 114.6 | 3375 | 3 | | 6 |
| 114.7 - 118.8 | 3500 | | | 7 |

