The risk of toxicity of deferasirox may be increased when inappropriately high doses are prescribed to patients with a low iron burden or with SF levels that are only slightly elevated. Detailed information regarding the correlation of toxicities and PK parameters (drug concentrations, C_{max}) is provided in the current [Investigators' Brochure].

A study of deferasirox was conducted in NTDT patients. Study No ICL670E2209, the THALASSA study, was a prospective, randomized, double-blind, placebo controlled trial of deferasirox with starting doses of 5 and 10 mg/kg/day in patients with NTDT.

The primary objective of this trial was to compare the efficacy of the two treatment groups of deferasirox based on the change in LIC (R2 MRI) from baseline after one year of treatment compared to placebo treated patients. One hundred and sixty-six patients with thalassemia intermedia (n=95), α -thalassemia (n=22) or HbE/ β -thalassemia (n=49) were randomized to starting deferasirox doses of 5 mg/kg/day (n=55) or matching placebo (n=28) and 10 mg/kg/day (n=55) or matching placebo (n=28). The average actual deferasirox dose (mean \pm SD) was 5.6 \pm 1.4 and 11.5 \pm 2.9 mg/kg/day, respectively. The primary objective of this trial was met. After one year of treatment with deferasirox, LIC significantly decreased by -1.95 mg Fe/g dw (95% CI: -2.94, -0.96; BL: 13.11) and -3.80 mg Fe/g dw (95% CI: -4.76, -2.85; BL: 14.56) in the deferasirox 5 and 10 mg/kg/day groups, respectively, compared with an increase of 0.38 mg Fe/g dw (95% CI: -0.59, 1.34; BL: 15.94) in the placebo; the difference between deferasirox 5 and 10 mg/kg/day groups vs placebo was significant (-2.33 mg Fe/g dw, $P=0.001$ and -4.18 mg Fe/g dw, $P<0.001$, respectively). After one year of treatment, the percentage of patients with LIC decrease ≥ 3 mg Fe/g dw from baseline was greater in the deferasirox 5 and 10 mg/kg/day cohorts (32.7% and 56.4%) compared to placebo (10.7%). In addition, more patients in deferasirox 5 and 10 mg/kg/day cohorts achieved LIC reduction $\geq 30\%$ from baseline (25.5% and 49.1%) compared to placebo (1.8%). The significant difference in the change in LIC from baseline between the 5 and 10 mg/kg/day group, -1.95 vs -3.80, $p=0.009$, justifies the starting dose of 10 mg/kg/day in this trial.

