6.4.2 Change in serum ferritin

If the serum ferritin level decreases to < 300 ng/mL at any visit, study drug will be held and the LIC will be assessed by R2 MRI. If repeat serum ferritin is < 300 ng/mL, treatment with the study drug will be interrupted. Repeat serum ferritin may be done locally, within two weeks of scheduled visit. If LIC is ≥ 5 mg Fe/g dw and repeat serum ferritin is ≥ 300 ng/mL, study drug treatment will be restarted at the same dose. Study drug will be held until LIC is ≥ 5 mg Fe/g dw and serum ferritin is ≥ 300 ng/mL. Study drug treatment will be restarted at the same dose (maximum restart dose of 10 mg/kg/day). The investigator will record this change on the dosage administration record eCRF and will notify Novartis at the time such a dose interruption is made, in order to facilitate optimal safety monitoring.

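### The dosing rule for LIC 3 to 7 cannot be followed literally by a patient above 10 mg/kg/day, and the restart rules after low ferritin do not agree

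*Protocol*

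**What the plan says.** **Assigned doses.** All patients start at 10 mg/kg/day. At Week 4, Protocol 6.1.1 prescribes "20 mg/kg/day for patients with baseline LIC > 15 mg Fe/g dw" and "15 mg/kg/day for patients with baseline LIC > 7 but ≤ 15 mg Fe/g dw"; patients with baseline LIC 5 to 7 stay at 10.

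**Six-monthly reviews from Week 24.** There is one rule per LIC band:
- Above 15: "Increase dose by 5-10 mg/kg/day if LIC is > 15 mg Fe/g dw, maximum of 30 mg/kg/day".
- Above 7 and up to 15: an optional increase of 5, maximum 20.
- From 3 to 7: "Same dose if LIC is ≥ 3 but ≤ 7 mg Fe/g dw, maximum of 10 mg/kg/day". Protocol 4.1 has the same rule ("Same dose if LIC is ≥3 but ≤ 7 mg Fe/g dw, maximum of 10 mg/kg/day"), and so does SAP 1.1. Protocol 6.4.3, on change in LIC, only refers back to 6.1.1.

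**Interruption and restart.** Protocol 6.1.1 interrupts treatment when LIC is below 3 or ferritin is below 300 ng/mL, with no repeat test. It restarts at the previous effective dose, with a maximum of 10, once LIC is at least 5 and ferritin at least 300. Protocol 4.1 and SAP 1.1 say the same.

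Protocol 6.4.2 adds a repeat ferritin. If LIC is at least 5 and the repeat is at least 300, it says "study drug treatment will be restarted at the same dose. Study drug will be held until LIC is", and that first restart carries no cap. After the hold-until condition, which names the same two thresholds, it says "Study drug treatment will be restarted at the same dose (maximum restart dose of 10 mg/kg/day".

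**The concern.** The LIC 3 to 7 rule is consistent only for a patient already at or below 10 mg/kg/day. From Week 4, patients with baseline LIC above 7 are assigned more than that, and those who respond well are the ones who enter the band. Two investigators could read the same sentence and assign different doses.

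The restart text has a similar gap. After a single low ferritin that the repeat does not confirm, 6.4.2 can be read as resuming the full dose, while 6.1.1 caps the restart.

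Both gaps arise when iron is lower. Protocol 1.2.1.2 itself warns: "The risk of toxicity of deferasirox may be increased when inappropriately high doses are prescribed to patients with a low iron burden". The first LIC-based decision falls at Week 24, before the Week 52 primary endpoint. The ambiguity therefore touches the regimen behind the primary result as well as the long-term LIC analyses.

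**Working it through.** There is no sample size, power or error-rate figure to reproduce. The check compares the texts and lists the dose that each reading gives.

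**LIC 3 to 7 band.** The inputs are the Week 4 doses and six-monthly rules in Protocol 6.1.1. It is assumed that no dose was reduced for safety. Reading A takes the maximum as a ceiling that lowers the current dose. Reading B leaves the current dose unchanged. Doses are in mg/kg/day.

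| First review with LIC 3 to 7 | LIC at earlier assessments | A | B |
|---|---|---|---|
| Week 24 | baseline > 15 | 10 | 20 |
| Week 24 | baseline > 7 to 15 | 10 | 15 |
| Week 24 | baseline 5 to 7 | 10 | 10 |
| Week 52 | > 15, then > 7 to 15 | 10 | 20 |
| Week 52 | > 7 to 15 twice | 10 | 15, or 15 + 5 = 20 |
| Week 52 | > 7 to 15, then > 15 | 10 | 15 + 5 = 20, or 15 + 10 = 25 |
| Week 52 | > 15 twice | 10 | 20 + 5 = 25, or 20 + 10 = 30 |
| Week 76 | baseline > 7, any path | 10 | 15 to 30 |

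The ordinary ratios are 15/10 = 1.5 and 20/10 = 2. Ratios of 25/10 = 2.5 and 30/10 = 3 need one of two conditions:
- a fall from above 15 to 7 or less between consecutive scans, that is, more than 15 − 7 = 8 mg Fe/g dw in about six months; or
- the maximum of 20 in the middle band also being read as not lowering the current dose.

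For scale, SAP section 1 reports a mean change of −6.68 (SD 7.018) over 52 weeks. A fall of that size in half the time is well beyond the mean, but the spread does not rule it out.

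**Restart.** Take a patient on 20 mg/kg/day with one ferritin below 300, a repeat of at least 300, and LIC of at least 5.

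| Text | Is a repeat needed before interruption? | Restart dose |
|---|---|---|
| 6.4.2, first restart sentence | yes | 20 |
| 6.4.2, last restart sentence | not stated | 10 |
| 6.1.1 (also 4.1 and SAP 1.1) | no | 10 |

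**Analyses touched.** SAP 2.2.1 groups average actual daily dose at cut-points 7.5, 12.5 and 17.5. Constant doses of 10, 15 and 20 fall in three different groups. The reading applied could thus move a patient between groups, depending on the time spent at each dose.

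**The case against.** A coherent reading exists for each text.

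The three six-monthly rules share one form, an action followed by a band maximum (30, 20, 10), and they are introduced as dose adjustments. Read in parallel, the last maximum is a ceiling that qualifies the unchanged dose. Figure 4-1, which the amendment log says was replaced to reflect the dose-adjustment clarification, is not visible here and may settle the matter.

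In 6.4.2 the two restart sentences are separated by the hold-until sentence, and only the first refers to a repeat ferritin. Taken in order, the first fits an unconfirmed low ferritin and the second a confirmed interruption. The sponsor must also be notified of each ferritin-based interruption, which limits drift in practice. Finally, the safety-by-dose tables use the dose actually taken, so patients are not misclassified, and the regimen already leaves investigators some discretion.

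Much of this stands, and it narrows the point. What remains is that neither reading is written down. The ceiling reading still needs the reader to set aside the instruction to keep the dose. The confirmed-versus-unconfirmed reading works inside 6.4.2 but conflicts with 6.1.1, which has no repeat step and caps the restart.

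**Conclusion.** The point holds as a wording inconsistency with consequences for dose. For a patient above 10 mg/kg/day whose LIC falls to 3 to 7, the visible text supports 10 or the current dose, usually 15 or 20. Doses of 25 to 30 are reachable only by the less common paths above. On restart after an unconfirmed low ferritin, the text supports either the full previous dose or 10. This assumes that Figure 4-1 does not settle the question and that the patient has not already been reduced to 10 or below for safety.

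A reader might infer more than the documents support:
- That doses differed between sites. The wording permits it, but no between-site data are given.
- That every responder with baseline LIC above 7 is affected. Patients already reduced for safety, and those who pass straight below 3, are not caught by the LIC 3 to 7 rule.
- That about 40% of patients meet the conflict, from the earlier trial's result in Protocol 1.2.1.2. That figure counts LIC below 5, includes patients below 3, and comes from a trial with starting doses of 5 or 10 escalated to at most 20.
- That the Week 52 result is biased. The ambiguity leaves the tested regimen less well defined, but neither the direction nor the size of any effect can be computed from the documents.

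**What to change.** Reconcile Protocol 4.1, 6.1.1 and 6.4.2 and SAP 1.1 so that together they state:
1. one rule for a patient above 10 mg/kg/day whose LIC falls to 3 to 7, saying whether the dose is kept or changed;
2. whether a repeat ferritin is needed before treatment is interrupted;
3. which restart sentence applies to which situation, and whether the cap applies after an unconfirmed low ferritin.

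Figure 4-1 should be checked against the agreed wording. Which rule is right is for the sponsor's clinical team.

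The cost is wording only: no new data and no change to the sample size or the analysis. Under Protocol 12.1 it does need a written amendment approved by the sponsor, the ethics committees and, where required, the health authorities. SAP 1.1 should then be brought into line.

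### Table 6-5 (25 mg/kg/day), 27.6-32.5 kg row: the tablets listed add up to 1000 mg, not the stated 750 mg, and exceed the 30 mg/kg/day study maximum

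*Protocol*

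**What the plan says.** Protocol Section 6.1.1 sets the daily dose by body weight, and Tables 6-1 to 6-6 turn each dose level into counts of 125, 250 and 500 mg tablets. The rounding rule is that the "daily dose will be rounded to the nearest whole tablet size (relative to a 125 mg tablet"). Section 6.4.1 tells sites to go back to the same tables whenever weight changes.

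The row at issue, in Table 6-5 (25 mg/kg/day), reads "27.6 - 32.5 | 750 | | 2 | 1". The columns are weight, closest dose, then the 125, 250 and 500 mg counts.

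Three other rows help to place it:
- Table 6-4 (20 mg/kg/day) builds 750 mg as "34.5 - 40.6 | 750 | | 1 | 1".
- Table 6-5 itself reaches 1000 mg at "37.6 - 42.5 | 1000 | | | 2".
- Table 6-6 (30 mg/kg/day) covers most of the same weight band with "27.2 - 31.3 | 875 | 3 | | 1".

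The dose level is reached through the LIC rule that applies from Week 24: "Increase dose by 5-10 mg/kg/day if LIC is > 15 mg Fe/g dw, maximum of 30 mg/kg/day". The ceiling is stated separately: "The maximum dose of deferasirox throughout the study will be 30 mg/kg/day".

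**The concern.** The dose column and the tablet columns of one row give different doses, and sites dispense from the tablet columns. If staff follow the tablets, the patient receives a dose above the study maximum.

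Patients are eligible from age 10 (Section 5.2) and 20 kg (Section 5.4), so the patient at risk would be small and probably a child. Section 1.2.1.2 describes the gastrointestinal, skin and creatinine effects of deferasirox as dose-dependent.

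The statistical stake is secondary. If 1000 mg was dispensed while 750 mg was recorded, that patient's actual dose would be understated in the exposure summaries, and possibly in the average-actual-dose categories of SAP Section 2.2.1.

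**Working it through.** **Inputs.** All rows of Tables 6-1 to 6-6, the 125 mg rounding rule and the 30 mg/kg/day maximum, all from Protocol Section 6.1.1.

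**1. Do the tablets make the stated dose?** For each row, sum = 125 × n125 + 250 × n250 + 500 × n500, compared with the closest-dose column. The six tables have 5 + 8 + 13 + 17 + 21 + 24 = 88 rows. In 87 the sum equals the stated dose. The exception is the 27.6-32.5 kg row of Table 6-5:

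2 × 250 + 1 × 500 = 1000 mg, against 750 mg stated; 1000 / 750 = 1.33.

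**2. Which figure is wrong?**
- At 30 kg, 25 × 30 = 750 mg.
- Rounding to the nearest 125 mg gives 750 mg between 687.5 and 812.5 mg. At 25 mg/kg these limits are 687.5 / 25 = 27.5 kg and 812.5 / 25 = 32.5 kg, which are the edges of the printed band. The stated dose is therefore reproduced.
- The 750 mg rows in Tables 6-2, 6-3, 6-4 and 6-6 all use 1 × 250 + 1 × 500.
- Table 6-5 assigns 1000 mg only from 37.6 to 42.5 kg, as 2 × 500.

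The dose is right and the 250 mg count is wrong.

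**3. What would be given if the tablet columns were followed?**

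| Weight (kg) | 25 mg/kg (mg) | 750 mg, in mg/kg | 1000 mg, in mg/kg | Table 6-6 dose (mg) |
|---|---|---|---|---|
| 27.6 | 690 | 27.2 | 36.2 | 875 |
| 30.0 | 750 | 25.0 | 33.3 | 875 |
| 31.3 | 782.5 | 24.0 | 31.9 | 875 |
| 31.4 | 785 | 23.9 | 31.8 | 1000 |
| 32.5 | 812.5 | 23.1 | 30.8 | 1000 |

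The 1000 mg dose is above 30 mg/kg/day across the whole band. From 27.6 to 31.3 kg it is also above the dose in the 30 mg/kg/day table, by 1000 / 875 = 1.14, or 14%. From 31.4 to 32.5 kg it equals that table's rounded dose.

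**4. Is this within what rounding already allows?** The highest rounded dose in Table 6-6 is 750 / 23.0 = 32.6 mg/kg/day. The 1000 mg dose exceeds that below 1000 / 32.6 = 30.7 kg, so in more than half of the band it is outside anything the rounding scheme produces.

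**5. With the correction.** 1 × 250 + 1 × 500 = 750 mg, or 23.1 to 27.2 mg/kg/day.

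**The case against.** Five points can be made for the plan.

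- **Another reading of the slip.** A 2 meant for the 125 mg column would also give 750 mg (2 × 125 + 500), and Tables 6-2 and 6-3 build 250 mg that way at low weights. The protocol text was read from a PDF, so a shifted cell cannot be wholly excluded. However, the row has the right number of cells, its neighbours read correctly, and no other 750 mg row is built with 125 mg tablets. If the printed row does show a 2 under 250 mg, it is wrong whatever its origin, and either correction restores 750 mg.
- **The right dose is printed.** The 750 mg is in the adjoining cell, and Section 6.1.1 starts from the calculated daily dose. This stands: an overdose is not the default outcome.
- **Few patients could be affected.** One would need a weight of 27.6-32.5 kg, an LIC above 15 mg Fe/g dw at Week 24 or later, and a move to 25 rather than 30 mg/kg/day. This also stands; the documents do not show that such a patient existed.
- **Monitoring exists.** Escalation brings weekly creatinine for four weeks and liver tests at two weeks. These may detect harm but do not prevent the wrong dose.
- **Tablet counts would show it.** The protocol says "The number of tablets of each strength dispensed will be recorded in the study drug dosing log", and the compliance measure in Section 10.3 compares prescribed with taken amounts from tablets dispensed and returned, so the error would appear as about 133%. But SAP Section 2.4.1 takes the percentage of planned dose from the DAR (presumably the dosage administration record). If 750 mg was entered there, that figure would look normal.

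**Conclusion.** The row is wrong as printed. Its tablets total 1000 mg against a correct 750 mg, 33% too high, and would deliver 30.8 to 36.2 mg/kg/day where the study allows at most 30. It is the only one of 88 rows that does not add up.

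It should be fixed because these tables are the dispensing instruction and the error runs towards overdose in small patients. The practical reach is probably small and may be nil. It depends on a site following the tablet columns over the dose column, and on a patient of that weight reaching 25 mg/kg/day. The primary analysis, the sample size and the design are untouched. Exposure data are affected only if tablets dispensed and dose recorded disagree.

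The log for Amendment 2 lists a corrected tablet count in Table 6-6 and a corrected weight range in Table 6-1, but no change to Table 6-5. The sponsor has therefore already treated errors of this kind as worth correcting.

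**What to change.** 1. In Table 6-5, row 27.6-32.5 kg, change the 250 mg count from 2 to 1 and leave 750 mg as it is, after a glance at the printed table to confirm the cell.
2. Notify sites.
3. For any patient of 27.6-32.5 kg assigned 25 mg/kg/day, compare the study drug dosing log with the dosage administration record.
4. Only where 1000 mg was dispensed and 750 mg recorded, correct that patient's actual dose from the tablets dispensed and returned.

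The cost is one digit, one site letter and a targeted look at records already kept. No design or analysis text changes.
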